The molar relationship should be overcorrected by approximately 2 mm. Overcorrection is considered a prepared anchorage to compensate for anchorage loss during retraction of premolars, canines and incisors. Forward movement of the molars to the class I position helps to upright the molars. The overjet increased as a result of anchorage loss. Gianelly recommended the placement of 100gm. class II elastics if the overjet increased by more than 2mm. If the second molars are present and the distalization rate is less than 1mm/month, and / or anchorage loss is excessive, he suggested sequential distalization or changing the treatment plan to extraction protocol. He recommended extraction of the third molars if they have erupted or close to erupt as they impede the distal movement of the first molars ^(8,9).

Recently, temporary anchorage devices have been used during upper molar distal movement. They eliminate the reactive forces from the distal force appliance, these prevent the side effects on the anterior anchoring teeth ⁽³⁾.

In 2004, Gelgör et al. investigated the skeletal, dental, and soft tissue changes after using intraosseous screw-supported distalization appliance. The maxillary first molars were distalized efficiently into an over corrected class I relationship. The force system passed occlusal to the center of resistance of the maxillary first molars, producing backward and upward movements and distal crown tipping. The distal movement of the maxillary molars did

not tend to open the mandible due to the intrusive effect. The status of the maxillary second molar or patient age, has no role on the effectiveness of distalization. There was a slight anchorage loss represented by maxillary incisor proclination and increased overjet. This anchorage loss resulted from mesial tipping of the first premolar, which may be caused by instability of the screw, bone elasticity, flexibility of the TPA, or insufficient connection between the TPA and the screw. Gelgör et al, concluded that 88 % of the space created was from molar distalization and the remaining 12 % resulted from reciprocal anchorage loss ⁽¹⁰⁾.

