In 2011, Fudalej et al. evaluated the effectiveness of the distalization of molars with temporary skeletal anchorage device (TSAD) and compared the effectiveness of the TSAD reinforced distalizers with tooth-born noncompliance distalizers. The authors findings indicate that the use of TSAD supported distalizers increased the amount of molar distalization, while the maxillary incisors remained stable. They suggested that in patients with TSAD, greater distal tipping of molars might be the result of excessive pressure exerted on the molars by the distalizers as the whole amount of force will act on the molars and no force will dissipate in the anterior direction. Skeletal anchorage system (SAS) showed the slowest distalization rate as the whole maxillary dentition was distalized simultaneously. They also found that, when implant or mini-plate supported distalization appliances are used; presence or absence of the second molars might play a smaller role. Because of the stability of the implant, no forces will dissipate within anterior direction causing mesial movement or tipping of the maxillary incisors ⁽¹¹⁾.

In 2013, a meta-analysis compared the amounts of distalization and anchorage loss of conventional and skeletal anchorage methods in class II malocclusion correction with intraoral distalizers. The authors concluded that variation in distalization time (1.5 – 14.16 months) might be due to variations in the amount of force applied by each appliance and in the severities of class II malocclusion which required different amounts of distalization. Both conventional and bone-anchored systems were effective for molar distalization but they differed in anchorage loss. Intraoral distalizers with conventional anchorage showed anchorage loss because the Nance button and the anterior teeth can't resist the reaction forces of distalization so they move in the opposite direction. Indirect skeletal anchor devices showed an amount of anchorage loss which is smaller than that with conventional distalizing device. This anchorage loss is the result of many factors such as reaction force, bone elasticity or absence of osseointegration of the mini-implant allowing their movement, flexibility of the wire connecting the premolar-mini-implant. Direct skeletal anchor devices allowed spontaneous distal movement of the premolars without anchorage loss probably due to stretching of the inter-septal fibers ⁽¹²⁾.

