- Leveling of these segments will be carried out using orthodontic wires sequentially, till 0.019" x 0.025" stainless steel archwire is reached.
- Segmented stiff 0.019" x 0.025" stainless steel archwire will be used to minimize the distal tipping and rotation of the molars. It will be extended from the maxillary second molar to the maxillary first premolar.
- In the first approach, a nickel titanium open coil spring will be inserted mesial to the maxillary first molar to provide distalizing force. In the second approach, two pieces of nickel titanium open coil springs will be inserted mesial to the maxillary first molar and mesial to the maxillary second molar.
- Mini screw anchorage system will be used as a mean of indirect anchorage.
- The patients will be seen every four weeks for reactivation until Class I molar relationship is obtained, as assessed clinically.

Methods of assessment:

- The rate of tooth movement will be analyzed using computer software on digital models obtained every four weeks. When a Class I molar relationship is obtained distalization will be considered achieved, which will be assessed clinically.
- Cone beam computed tomography (CBCT) will be taken for every patient pre-treatment and post-distalization.

Adverse event reporting

Anticipated adverse effects regarding the use of mini screw and its remedy

1. **Pain and discomfort:** If present, it may last 1–2 days and could be reduced by instructing the patient to use warm mouth rinse containing local anesthetic agent.
2. **Irritation to the buccal mucosa:** Bonding resin or a periodontal wound dressing could be applied to the head of the mini screw to smooth its surface and to minimize soft-tissue irritation.
3. **Inflammation around mini screw:** The screws need to be thoroughly cleaned. Mild infections can be controlled by using antiseptic mouthwash and by regular brushing.
4. **Mini screw mobility or failure:** The patient will be instructed to avoid manipulating the screw with fingers, tongue, or with foreign objects like pens. The mini screw could be tightened and left for 1–2 months with no loading, or light loading if necessary. If stability cannot be regained, the mini screw will be removed and replaced.

Statistical analysis

All gathered data will be tabulated and statistically analyzed.

References

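### The end of treatment and the second CBCT are tied to reaching Class I, so a randomised patient who stops short has no defined second scan, end date or outcome category

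*Protocol*

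**What the plan says.** **Protocol, Procedure.** Treatment is open-ended and stops on success: "The patients will be seen every four weeks for reactivation until Class I molar relationship is obtained, as assessed clinically".

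**Protocol, Methods of assessment.** The endpoint is the same clinical judgement: "When a Class I molar relationship is obtained distalization will be considered achieved, which will be assessed clinically". The second scan is placed relative to it: "Cone beam computed tomography (CBCT) will be taken for every patient pre-treatment and post-distalization". One record does not depend on success: "The rate of tooth movement will be analyzed using computer software on digital models obtained every four weeks".

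**Protocol, Adverse event reporting.** The section headed "Anticipated adverse effects regarding the use of mini screw and its remedy" is not limited to patients who reach Class I. For a screw that stays unstable it says: "If stability cannot be regained, the mini screw will be removed and replaced". It does not say how a patient is classified if treatment nevertheless ends early.

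**Protocol, Statistical analysis.** One general sentence, with nothing on missing post-treatment records, dropout or the analysis set.

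**SAP, Tests used.** Pre/post change is tested within arms by paired t-test. The change is compared between arms by Mann Whitney test. Duration is compared by independent t-test and is listed under Baseline characteristics, although it arises after randomisation. No table gives numbers randomised, reaching Class I or stopped.

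**The concern.** A scan timed after distalization, where distalization is complete only at Class I, has a definite date only for patients who succeed. For anyone else the plan leaves open whether the scan is taken, when, and under what label the patient is reported.

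The skeletal, dental and soft-tissue tables are pre/post differences, so a patient without a second CBCT cannot enter them. Duration has the same gap: a patient who never reaches Class I has no value for it, and a t-test cannot use the partial information that Class I had not been reached by the stop date.

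Randomisation protects a comparison of everyone randomised. It does not protect a comparison of those who succeeded if the chance of success differs between one spring and two. The plan also gives no way to report the share of patients in whom each approach reached Class I.

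**Working it through.** **1. The rule applied to two patients**

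| Item | Reaches Class I | Stops short |
|---|---|---|
| End of treatment | date Class I is judged | not defined |
| Second CBCT | after that date | not defined |
| Four-weekly digital models | yes | yes, up to stopping |
| Mini screw adverse events | covered | covered |
| Pre/post tables | enters | enters only if a second scan happens to exist |
| Duration | observed | no value, no censoring rule |
| Outcome category | distalization achieved | none |

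**2. The planned number.** The protocol plans 20 patients but gives no alpha, power, effect size, SD or dropout allowance. The 20 cannot be reproduced, and it contains no stated allowance for patients who stop.

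**3. Who is in the reported tables.** For a paired t-test, t = MD/(SD/√n) with n − 1 degrees of freedom, so n can be inferred from the reported MD, SD and p.

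- Group I at n = 12: SNB 0.196 (reported 0.194), U1-FHP 0.0419 (0.042), U5-FHP 0.0141 (0.014).
- Group II at n = 9: U4-FHP 0.0337 (0.034), U5-FHP 0.0079 (0.008), MBc6/S Ver 0.0040 (0.004).

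Of 20 rows tried, 17 fit 12 or 9 best. Of the other three:
- Group I MBc6/S Ver does not fit: it gives p < 0.0001 against 0.002 reported.
- Group I MBc7/S Ver is reported as 0.000 and cannot identify n.
- Group II SNB is barely sensitive to n: 0.7435 at 9 and 0.7293 at 10, against 0.735.

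Table 13 gives the same counts: 2 + 10 = 12 and 3 + 6 = 9. The total is 21, against 20 planned, and this is not explained. The tables therefore appear to hold complete pairs only. That is equally compatible with nobody stopping short and with such patients being left out.

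**4. Duration (Table 14).** Pooled SD = √[(11 × 2.90² + 8 × 3.89²)/19] = √(213.57/19) = 3.35. SE = 3.35 × √(1/12 + 1/9) = 1.48. t = (10.59 − 8.03)/1.48 = 1.73, so p = 0.0995 (Welch 0.119), against 0.09 reported. This is an uncensored comparison of 12 and 9 observed values. The Group I SD is itself impossible: with range 5.50 to 9.73 and mean 8.03, the largest SD at n = 12 is √(2.53 × 1.70 × 12/11) = 2.17, not 2.90. I therefore rest nothing on Table 14 beyond how Duration was analysed.

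**5. What an omitted patient could do (assumed values).** An omitted patient is not among the 12 or 9, so the share is 1/13 = 7.7% or 1/10 = 10%. Take U6-FHP (Table 23), where the arms differ by −13.54 − (−4.72) = −8.82°. Suppose one Group II patient had been left out:
- assumed change 0°: mean (9 × −13.54 + 0)/10 = −12.19, difference −7.47°
- assumed change −25°: mean (9 × −13.54 − 25)/10 = −14.69, difference −9.97°

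With three such patients the range is about −5.4° to −11.7°. The shift can go either way.

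**6. Could it arise at all (assumed rates).** The chance of at least one patient in 20 not reaching Class I is 1 − (1 − f)^20: 64%, 88% and 99% for f = 5%, 10% and 20%. The documents give no rate.

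**The case against.** Treating to Class I is a legitimate design: it compares both approaches at the same clinical result. The CBCT sentence covers every patient. Models are taken every four weeks whatever the outcome, mini screw events are recorded regardless of success, and a failed screw is to be replaced. No failure is documented, and 21 tabulated against 20 planned gives no sign of loss. The SAP nowhere restricts the analysis to patients who reached Class I. All of this stands, and it limits the point to the second CBCT, the end date and the outcome category. It does not close the gap, because an instruction to scan every patient after distalization gives no date when distalization never completes.

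A reader might infer more, in four ways that the documents do not support.

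- *That patients who stop have no later record, or that harms are seen only in successes.* The models and the adverse event section contradict this.
- *That the background shows failures were likely.* The passage beginning "If the second molars are present and the distalization rate is less than 1mm/month, and / or anchorage loss is excessive" reports one author's suggestion for coils with a Nance appliance, not a rule of this trial. The same background gives 0.37 mm per month for simultaneous first and second molar distalization. Rates formed from the SAP would be ratios of arm means, over a Duration that may include levelling.
- *That the longest course, 14.9 months, exceeds the published range ending at 14.16 months.* One is a single patient's maximum. The protocol does not say whether the other describes patients or study averages.
- *That one lost patient is 1/12 or 1/9 of an arm.* Someone left out of the tables is not in those denominators.

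**Conclusion.** The point holds in limited form and should be corrected. The second CBCT, end date and outcome category are defined only for patients who reach Class I, and the SAP tables do not show that the gap was filled later. Comparing CBCT-measured effects and Duration conditional on success follows from the rule; the SAP does not state it.

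The bias, if any, cannot be sized. It needs at least one omitted patient, and failure related to the approach. Its direction for tipping or anchorage loss is also open: a patient who stopped early may have moved little or tipped a great deal. It would therefore be wrong to conclude that either approach has been made to look safer. For Duration the direction within an arm is clearer: omitted patients had not reached Class I when they stopped, so their time to Class I is longer than their time on treatment. With arms of 12 and 9, a single omission carries a weight of 7.7% or 10%, enough to move a mean visibly under the assumed values above.

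**What to change.** - **Timing.** Take the already planned second CBCT and the final digital model at the end of distalization for any reason. Record the stop date, the reason and whether Class I was reached.
- **Flow.** Report by arm the numbers randomised, reaching Class I and stopped, with reasons. The SAP already presents results, so do this for those results too wherever clinical records allow, and explain 21 against 20.
- **Pre/post tables.** Include stopped patients where a second CBCT exists. Use the last four-weekly model only for crown-level measurements it can supply; it cannot give root-apex, FHP or skeletal measures.
- **Duration.** Move it out of the baseline section, define its start, and analyse it as time to Class I, censored at the stop date. Show the reasons for stopping beside it, because stopping may be related to slow progress.

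The cost is protocol and SAP wording, one end-of-distalization form and one table row, with no scan beyond the two already planned. The downside is that some CBCTs will be taken before Class I is reached, and the results may look less favourable. New wording cannot recover stops that were never recorded. Any time limit or clinical stopping rule is for the investigator to set.

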Document Date: June 23, 2022

Three Dimensional Assessment of Maxillary Molars Following Distalization Using Two Different Approaches

A Thesis
Submitted to Faculty of Dentistry
Ain-Shams University
In Partial Fulfillment of the Requirements of
Master's Degree in Orthodontics

Faculty of Dentistry
Ain Shams University
2022

Statistical analysis

Statistical analysis was performed with SPSS 20^{®*}, Graph Pad Prism^{®**}, and Microsoft Excel 2016^{***}.

All quantitative data were explored for normality by using Shapiro Wilk Normality test and presented as means and standard deviation (SD) values. All qualitative data were presented as frequency & percentage. All data were presented in (43) tables & (38) graphs.

Tests used:

- Comparisons 2 different groups was performed by using Mann Whitney test.
- Comparisons 2 successive follow ups periods was performed by using Paired t-test.
- Comparison between quantitative continuous data (Age & Duration) was performed by Independent t-test.
- Comparison between qualitative dichotomous data (Gender) was performed by Chi square test.
- Reliability test was performed by using Intra-class Correlation Coefficient (ICC).

* Statistical Package for Social Science, IBM, Armonk, NY, USA.

** Graph Pad Technologies, San Diego, CA, USA

*** Microsoft Co-operation, Redmond, WA, USA.

* All results presented as:

I. Normality test.

II. Baseline characteristics:

- A. Age.
- B. Gender.
- C. Duration
- D. Pretreatment measurements. (Appendix IV).

III. Measurements

The following measurements were carried for both group I and group II as well as in comparison between the two groups.

A. Skeletal measurements

- 1. Skeletal antero-posterior measurements.
- 2. Skeletal vertical measurements.

B. Dental measurements

- 1. Angular
- 2. Linear

C. Soft tissue measurements.

IV. Reliability: (Appendix V)

- A. Inter-observer.
- B. Intra-observer.

I. Normality test:

Exploration of the given data was performed using Shapiro-Wilk test and Kolmogorov-Smirnov test for normality. As Listed in (Table 11) and showed in (Figure 53), it was revealed that the significant level (P-value) was shown to be insignificant as P-value > 0.05 , which indicated that alternative hypothesis was rejected, and the concluded data originated from normal distribution (parametric data) resembling normal Bell curve in pre & post measurements while P value was significant in the difference between both groups which indicated nonparametric data.

Table (11): Normality exploration of both groups regarding all measurements:

Measurements		Group I Single Coil Spring	Group II Double Coil Spring
Skeletal.	Pre	> 0.05	> 0.05
	Post	> 0.05	> 0.05
	Difference	$< 0.05^*$	$< 0.05^*$
Dental	Pre	> 0.05	> 0.05
	Post	> 0.05	> 0.05
	Difference	$< 0.05^*$	$< 0.05^*$
Soft tissue	Pre	> 0.05	> 0.05
	Post	> 0.05	> 0.05
	Difference	$< 0.05^*$	$< 0.05^*$

* Significant difference as $P < 0.05$

[figure not shown]
[figure not shown]

Figure (53): Scattered chart represents normal bell curve of normality test.

II. Baseline characterized:

1. Age:

In group I, minimum age was (18.4), maximum was (21.2), while mean \pm standard deviation was (19.42 ± 1.03) . In group II, minimum age was (18.08), maximum was (23.17), while mean \pm standard deviation was (20.7 ± 2.24) , as presented in table (12) and figure (54).

Comparison between both groups was performed by using Independent t-test which revealed insignificant difference between them as $P > 0.05$, as presented in table (12).

Table (12): Minimum, maximum, mean & standard deviation of age in both groups:

	Min	Max	M	SD	P value
G I	18.4	21.2	19.42	1.03	0.09
G II	18.08	23.17	20.7	2.24	

N: count

Min: minimum

Max: maximum

M: mean

SD: standard deviation

[figure not shown]

Figure (54): Bar chart showing mean of age in both groups.

2. Gender:

In gender all companions were performed by using Chi square test. In group I, male (16.67%) was significantly lower than female (83.3%) as $P < 0.05$, while in group II male (33.3%) was insignificantly lower than female (66.6%) as $P > 0.05$, as presented in table (13) and figure (55).

Also, comparison between group I & II reveled insignificant difference between them in both male & female as $P > 0.05$ as presented in table (13).

Table (13): Frequency & percentage of gender distribution in both groups:

Group	Male		Female		P value
	N	%	N	%	
Group I	2	16.67%	10	83.33%	0.001*
Group II	3	33.33%	6	66.67%	0.13
P value	0.34		0.34		

N: count

%: percentage

P: probability level which is significant at $P \leq 0.05$

[figure not shown]

Figure (55): Bar chart showing percentage of gender distribution in both groups

3. Duration:

In group I, minimum duration was (5.5 months), maximum was (9.73 months), while mean \pm standard deviation was (8.03 ± 2.9) . In group II, minimum duration was (4 months), maximum was (14.9 months), while mean \pm standard deviation was (10.59 ± 3.89) .

Comparison between both groups was performed by using Independent t-test which revealed insignificant difference between them as $P>0.05$, as presented in table (14) and figure (56).

Table (14): Minimum, maximum, mean & standard deviation of duration in months in both groups:

	Min	Max	M	SD	P value
Group I	5.50	9.73	8.03	2.90	0.09
Group II	4.00	14.90	10.59	3.89	

M: mean SD: standard deviation

P: probability level which is significant at $P \leq 0.05$

[figure not shown]

Figure (56): Bar chart showing mean of duration in months in both groups.

III. Measurements:

A. Skeletal:

1. Anteroposterior:

- Group I:**

In group I pretreatment records, post treatment records and difference between them regarding anteroposterior skeletal measurements were presented in table (15) and figure (57).

Comparison between pretreatment & post treatment records was performed by using Paired t-test which revealed insignificant difference between them in all measurements as $P > 0.05$, as presented in table (15).

Table (15): Mean & standard deviation of pretreatment, post treatment records and difference between them regarding anteroposterior skeletal measurements in group I:

Group I Anteroposterior Skeletal Measurements	Pre		Post		Difference		P value
	M	SD	M	SD	M	SD	
SNA angle	83.41	4.33	83.47	3.90	0.05	1.26	0.854
SNB angle	77.98	3.18	77.44	2.53	-0.54	1.36	0.194
ANB angle	5.50	2.11	6.07	2.53	0.57	1.72	0.273
A-NV distance	6.79	4.69	6.96	3.87	0.17	1.11	0.611
Pog-NV distance	6.06	6.44	6.02	5.32	-0.04	2.20	0.951

M: mean SD: standard deviation

P: probability level which is significant at $P \leq 0.05$

[figure not shown]

Figure (57): Bar chart showing mean of pretreatment, post treatment records and difference between them regarding anteroposterior skeletal measurements in group I.

- **Group II:**

In group II pretreatment records, post treatment records and difference between them regarding anteroposterior skeletal measurements were presented in table (16) and figure (58).

Comparison between pretreatment & post treatment records was performed by using Paired t-test which revealed insignificant difference between them in all measurements as $P > 0.05$, as presented in table (16).

Table (16): Mean & standard deviation of pretreatment, post treatment records and difference between them regarding anteroposterior skeletal measurements in group II:

Group II Anteroposterior Skeletal Measurements	Pre		Post		Difference		P value
	M	SD	M	SD	M	SD	
SNA angle	83.64	4.14	83.62	4.15	-0.02	1.07	0.952
SNB angle	79.27	3.08	79.13	3.03	-0.14	1.24	0.735
ANB angle	4.36	1.72	4.49	1.63	0.12	0.54	0.517
A-NV distance	7.44	3.13	7.09	3.00	-0.35	0.74	0.195
Pog-NV distance	8.10	3.71	7.31	3.26	-0.79	2.04	0.277

M: mean SD: standard deviation

P: probability level which is significant at $P \leq 0.05$

[figure not shown]

Figure (58): Bar chart showing pretreatment, post treatment records and difference between them regarding anteroposterior skeletal measurements in group II.

- **Comparison between both groups:**

Comparison between group I & II regarding difference between pretreatment & posttreatment records of anteroposterior skeletal measurements was performed by using Mann Whitney test which revealed insignificant difference between them regarding all measurements, as presented in table (17) and figure (59).

Table (17): Comparison between both groups regarding anteroposterior skeletal measurements:

Difference Anteroposterior Skeletal Measurements	Group I		Group II		P value
	MD	SD	MD	SD	
SNA angle	0.05	1.26	-0.02	1.07	0.81
SNB angle	-0.54	1.36	-0.14	1.24	0.75
ANB angle	0.57	1.72	0.12	0.54	0.75
A-NV distance	0.17	1.11	-0.35	0.74	0.24
Pog-NV distance	-0.04	2.20	-0.79	2.04	0.11

MD: mean difference

SD: standard deviation

P: probability level which is significant at $P \leq 0.05$

[figure not shown]

Figure (59): Bar chart showing comparison between both groups regarding anteroposterior skeletal measurements.

2. Vertical:

- **Group I:**

In group I pretreatment records, post treatment records and difference between them regarding vertical skeletal measurements were presented in table (18) and figure (60).

Comparison between pretreatment & post treatment records was performed by using Paired t-test which revealed insignificant difference between them in all measurements as $P > 0.05$, as presented in table (18).

Table (18): Mean & standard deviation of pretreatment, post treatment records and difference between them regarding vertical skeletal measurements in group I:

Group I Vertical Skeletal Measurements	Pre		Post		Difference		P value
	M	SD	M	SD	MD	SD	
PP-SN angle	8.66	3.09	8.96	3.81	0.31	0.91	0.425
ANS-Me distance	63.77	4.78	63.81	5.66	0.04	1.43	0.924
MP-SN angle	36.91	4.09	36.76	4.20	-0.15	0.61	0.265

M: mean

SD: standard deviation

MD: mean difference

P: probability level which is significant at $P \leq 0.05$

[figure not shown]

Figure (60): Bar chart showing mean of pretreatment, post treatment records and difference between them regarding vertical skeletal measurements in group I.

- **Group II:**

In group II pretreatment records, post treatment records and difference between them regarding vertical skeletal measurements were presented in table (19) and figure (61).

Comparison between pretreatment & post treatment records was performed by using Paired t-test which revealed insignificant difference between them in all measurements as $P > 0.05$, as presented in table (19).

Table (19): Mean & standard deviation of pretreatment, post treatment records and difference between them regarding vertical skeletal measurements in group II:

Group II Vertical Skeletal Measurements	Pre		Post		Difference		P value
	M	SD	M	SD	MD	SD	
PP-SN angle	9.47	3.58	9.64	3.31	0.17	0.27	0.54
ANS-Me distance	65.55	4.86	65.04	5.93	-0.52	1.66	0.376
MP-SN angle	36.99	3.05	36.55	2.81	-0.44	1.40	0.377

M: mean

SD: standard deviation

MD: mean difference

P: probability level which is significant at $P \leq 0.05$

[figure not shown]

Figure (61): Bar chart showing mean of pretreatment, post treatment records and difference between them regarding vertical skeletal measurements in group II.

- **Comparison between both groups:**

Comparison between group I & II regarding difference between pretreatment & posttreatment records of vertical skeletal measurements was performed by using Mann Whitney test which revealed insignificant difference between them regarding all measurements, as presented in table (20) and figure (62).

Table (20): Comparison between both groups regarding vertical skeletal measurements:

Difference Vertical Skeletal Measurements	Group I		Group II		P value
	MD	SD	MD	SD	
PP-SN angle	0.31	0.91	0.17	0.27	0.66
ANS-Me distance	0.04	1.43	-0.52	1.66	0.24
MP-SN angle	-0.15	0.61	-0.44	1.40	0.61

SD: standard deviation

MD: mean difference

P: probability level which is significant at $P \leq 0.05$

[figure not shown]

Figure (62): Bar chart showing comparison between both groups regarding vertical skeletal measurements.

B. Dental

1. Angular

a. Anteroposterior

• Group I:

In group I pretreatment records, post treatment records and difference between them regarding anteroposterior- angular- dental measurements were presented in table (21) and figure (63).

Comparison between pretreatment & post treatment records was performed by using Paired t-test which revealed insignificant difference between them in all measurements as $P > 0.05$ except U1-FHP and U5-FHP (Post was significantly higher than prerecord) as $P < 0.05$, as presented in table (21).

Table (21): Mean & standard deviation of pretreatment, post treatment records and difference between them regarding anteroposterior angular dental measurements in group I:

Group I Anteroposterior Angular Dental Measurements	Pre		Post		Difference		P value
	M	SD	M	SD	MD	SD	
U1-NA	25.83	9.57	26.27	10.17	0.44	1.88	0.437
U1-FHP	123.54	12.59	124.50	12.88	0.97	1.46	0.042*
U4-FHP	102.14	9.64	103.24	11.70	1.10	4.80	0.444
U5-FHP	96.83	11.01	101.88	13.25	5.06	6.02	0.014*
U6-FHP	94.43	8.90	89.70	9.02	-4.72	9.69	0.119
U7-FHP	87.70	10.16	82.83	8.09	-4.87	8.16	0.063

M: mean

SD: standard deviation

MD: mean difference

P: probability level which is significant at $P \leq 0.05$

[figure not shown]

Figure (63): Bar chart showing mean of pretreatment, post treatment records and difference between them regarding anteroposterior angular dental measurements in group I.

- **Group II:**

In group II pretreatment records, post treatment records and difference between them regarding anteroposterior- angular- dental measurements were presented in table (22) and figure (64).

Comparison between pretreatment & post treatment records was performed by using Paired t-test which revealed insignificant difference between them in all measurements as $P > 0.05$ except U4-FHP and U5-FHP (Post records were significantly higher than prerecords), and U6-FHP (Post record was significantly lower than prerecord) as $P < 0.05$, as presented in table (22).

Table (22): Mean & standard deviation of pretreatment, post treatment records and difference between them regarding anteroposterior angular dental measurements in group II:

Group II Anteroposterior Angular Dental Measurements	pre		post		Difference		P value
	M	SD	M	SD	MD	SD	
U1-NA	16.88	4.94	17.05	5.79	0.18	0.85	0.67
U1-FHP	114.61	4.00	115.05	4.83	0.43	0.83	0.44
U4-FHP	105.26	5.30	109.68	4.81	4.42	5.18	0.034*
U5-FHP	102.27	4.80	108.52	5.79	6.25	5.34	0.008*
U6-FHP	97.77	1.80	84.23	9.21	-13.54	8.61	0.002*
U7-FHP	88.47	8.81	80.17	9.62	-8.30	0.81	0.077

M: mean

SD: standard deviation

MD: mean difference

P: probability level which is significant at $P \leq 0.05$

[figure not shown]

Figure (64): Bar chart showing pretreatment, post treatment records and difference between them regarding anteroposterior angular dental measurements in group II.

- **Comparison between both groups:**

Comparison between group I & II regarding difference between pretreatment & posttreatment records of anteroposterior angular dental measurements was performed by using Mann Whitney test which revealed insignificant difference between them regarding all measurements except U6-FHP (Group I was significantly higher than group II) as $P < 0.05$, as presented in table (23) and figure (65).

Table (23): Comparison between both groups regarding anteroposterior angular dental measurements:

Difference Anteroposterior Angular Dental Measurements	Group I		Group II		P value
	MD	SD	MD	SD	
U1-NA	0.44	1.88	0.18	0.85	0.70
U1-FHP	0.97	1.46	0.43	0.83	0.33
U4-FHP	1.10	4.80	4.42	5.18	0.82
U5-FHP	5.06	6.02	6.25	5.34	0.61
U6-FHP	-4.72	9.69	-13.54	8.61	0.03*
U7-FHP	-4.87	8.16	-8.30	0.81	0.16

SD: standard deviation

MD: mean difference

P: probability level which is significant at $P \leq 0.05$

[figure not shown]

Figure (65): Bar chart showing comparison between both groups regarding anteroposterior angular dental measurements.

b. Rotation

- **Group I:**

In group I pretreatment records, post treatment records and difference between them regarding rotation- angular- dental measurements were presented in table (24) and figure (66).

Comparison between pretreatment & post treatment records was performed by using Paired t-test which revealed insignificant difference between them in all measurements as $P > 0.05$ except U5-MSP and U7-MSP as there was a statistical significant difference as $P < 0.05$ (Post was significantly higher than prerecord), while in U6-MSP there was a highly statistical significant difference as $P < 0.001$ (Post was significantly higher than prerecord) as presented in table (24).

Table (24): Mean & standard deviation of pretreatment, post treatment records and difference between them regarding rotation angular dental measurements in group I:

Group I Rotation Angular Dental Measurements	Pre			Post			P value
	M	SD	M	SD	MD	SD	
U4-MSP	71.89	6.73	74.95	6.62	3.06	8.70	0.248
U5-MSP	68.84	7.63	63.36	7.23	-5.48	4.79	0.002*
U6-MSP	32.38	6.45	50.50	10.29	18.12	8.35	0.000**
U7-MSP	42.42	9.67	53.25	11.15	10.84	8.06	0.001*

M: mean

SD: standard deviation

MD: mean difference

P: probability level which is significant at $P \leq 0.05$

[figure not shown]

Figure (66): Bar chart showing pretreatment, post treatment records and difference between them regarding rotation angular dental measurements in group I.

- **Group II:**

In group II pretreatment records, post treatment records and difference between them regarding rotation- angular- dental measurements were presented in table (25) and figure (67).

Comparison between pretreatment & post treatment records was performed by using Paired t-test which revealed insignificant difference between them in all measurements as $P > 0.05$ except U5-MSP and U6-MSP as there was a statistical significant difference as $P < 0.05$ (Post was significantly higher than prerecord), as presented in table (25).

Table (25): Mean & standard deviation of pretreatment, post treatment records and difference between them regarding rotation angular dental measurements in group II:

Group II Rotation Angular Dental Measurements	pre		post		Difference		P value
	M	SD	M	SD	MD	SD	
U4-MSP	74.75	5.74	75.51	7.01	0.76	7.22	0.761
U5-MSP	76.26	10.52	56.45	9.88	-19.81	11.69	0.001*
U6-MSP	32.33	6.82	51.46	19.53	19.13	19.26	0.018*
U7-MSP	37.63	6.55	64.09	13.42	26.47	6.87	0.057

M: mean

SD: standard deviation

MD: mean difference

P: probability level which is significant at $P \leq 0.05$

[figure not shown]

Figure (67): Bar chart showing mean of pretreatment, post treatment records and difference between them regarding rotation angular dental measurements in group II.

- **Comparison between both groups:**

Comparison between group I & II regarding difference between pretreatment & posttreatment records of rotation - angular dental measurements was performed by using Mann Whitney test which revealed insignificant difference between them regarding all measurements except U5-MSP (Group I was significantly higher than group II) as $P < 0.05$, as presented in table (26) and figure (68).

Table (26): Comparison between both groups regarding rotation angular dental measurements:

Difference Rotation Angular Dental Measurements	Group I		Group II		P value
	MD	SD	MD	SD	
U4-MSP	3.06	8.70	0.76	7.22	0.75
U5-MSP	-5.48	4.79	-19.81	11.69	0.009*
U6-MSP	18.12	8.35	19.13	19.26	0.45
U7-MSP	10.84	8.06	26.47	6.87	0.06

SD: standard deviation

MD: mean difference

P: probability level which is significant at $P \leq 0.05$

[figure not shown]

Figure (68): Bar chart showing comparison between both groups regarding rotation angular dental measurements.

c. Crown inclination

- **Group I:**

In group I pretreatment records, post treatment records and difference between them regarding crown inclination- angular- dental measurements were presented in table (27) and figure (69).

Comparison between pretreatment & post treatment records was performed by using Paired t-test which revealed insignificant difference between them in all measurements as $P > 0.05$ except U4 and U5 as there was a statistically significant difference as $P < 0.05$ (Post was significantly higher than prerecord), as presented in table (27).

Table (27): Mean & standard deviation of pretreatment, post treatment records and difference between them regarding crown inclination - angular dental measurements in group I:

Group I Crown Inclination Angular Dental Measurements	Pre		Post		Difference		P value
	M	SD	M	SD	MD	SD	
U4	4.80	2.34	11.94	7.12	7.14	7.61	0.008*
U5	6.47	4.23	13.79	7.28	7.32	6.86	0.004*
U6	4.84	4.06	4.81	2.95	-0.03	3.87	0.980
U7	5.76	3.65	7.94	7.83	2.19	5.81	0.219

M: mean

SD: standard deviation

MD: mean difference

P: probability level which is significant at $P \leq 0.05$

[figure not shown]

Figure (69): Bar chart showing mean of pretreatment, post treatment records and difference between them regarding crown inclination - angular dental measurements in group I.

- **Group II:**

In group II pretreatment records, post treatment records and difference between them regarding crown inclination- angular- dental measurements were presented in table (28) and figure (70).

Comparison between pretreatment & post treatment records was performed by using Paired t-test which revealed significant difference between them in all measurements as $P < 0.05$ except U5 as there was a statistical insignificant difference as $P > 0.05$ (Post was significantly higher than prerecord), as presented in table (28).

Table (28): Mean & standard deviation of pretreatment, post treatment records and difference between them regarding crown inclination - angular dental measurements in group II:

Group II Crown Inclination Angular Dental Measurements	pre		post		Difference		P value
	M	SD	M	SD	MD	SD	
U4	5.11	3.82	12.77	6.01	7.66	7.31	0.014*
U5	8.28	5.27	14.25	7.50	5.98	8.45	0.067
U6	2.99	1.67	7.12	4.47	4.13	3.66	0.010*
U7	5.23	4.77	9.23	6.85	3.99	5.11	0.047*

M: mean SD: standard deviation

MD: mean difference

P: probability level which is significant at $P \leq 0.05$

Crown inclination / Angular Dental Measurements Group II

[figure not shown]

